6.7.2 Planned Analyses

An eligible population will include all inebilizumab users identified during the study period in the selected data sources. From the eligible population, the population for analysis will be created by applying the study inclusion criteria, as defined in [section 6.2.1](#). The number and proportion of patients not included in the study for specific reasons will be presented in a STrengthening the Reporting of OBServational studies in Epidemiology (STROBE) (37) diagram.

All analyses will be conducted for the overall study population and in sub-groups of special interest: patients concomitantly receiving other immunosuppressive agents ([Table 9](#) and [Table 10](#) in Annex 3), and patients aged >65 years at the index date, if the sample size permits. Further details for the sample size required to conduct each of the analysis will be provided in the SAP.

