6 RESEARCH METHODS

6.1 Study Design

This will be a non-interventional multi-center cohort study of patients initiating inebilizumab conducted with secondary data sources in France, Germany, Italy, the Netherlands, and Spain. The study will be based on a cohort-event monitoring design to capture both drug utilization and selected safety outcomes in patients initiating inebilizumab. The proposed study design allows for an efficient initial descriptive evaluation of AESI.

The **study period** in individual countries will start on different dates, depending on the launching time of the drug (the earliest in the second quarter of 2022) (Table 1). The end of the study period will be also country-specific (the latest in December 2027) and will depend on the dates of data availability in individual data sources (different lag times and data release dates).

Table 1 Study periods, by country

	France	Germany	Italy	Netherlands	Spain
	SNDS/ NOMADMUS	GKV	RISM	PHARMO	SIDIAP
Launch date (quarter, year)	Q2, 2022	Q3, 2022	Q2 2023	Q3, 2023	Q2, 2023
Start of study period	May 2022	Aug 2022	May 2023	Aug 2023	May 2023
End of study period	Dec 2026	Dec 2026	Dec 2027	Dec 2026	Sep 2027
Study period duration (months)	57	54	56	41	53

Q2, 2nd quartile; Q3, 3rd quartile

The study population will be constituted by a cohort of adult female and male patients diagnosed with NMOSD with entry trigger by inebilizumab initiation.

[figure not shown]
The **index date** (Day 0) will be defined as the date of first treatment (date of administration/prescription/dispensation, depending on data available in selected data sources) (Figure 1). Patients initiating the treatment will be identified throughout the study period. After the index date, enrolled patients will be followed for 12 months or censored at end of study period or loss of follow-up (death, disenrollment/de-registering) whichever occurs first.

A **baseline period**, including any time from when data are available up to the index date, will be used to establish comorbidities and NMOSD-related clinical characteristics, whereas a short period of 6 months prior to or at index date will be used to determine previous immunosuppressive therapies.

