History of relapses will be ascertained depending on available data in the data sources (e.g., using documented relapse episodes as defined by individual disease-specific registries or considering the previous use of acute treatments such as intravenous corticosteroids, intravenous immunoglobulin or plasmapheresis therapy, or hospital admission with selected principal diagnoses) and will be defined in detail in SAP. Patients will be characterized according to the number of relapses in the previous 1 and 2 years (none, one, two or more).

Baseline use of **acute treatments** will include intravenous corticosteroids, intravenous immunoglobulin or plasmapheresis therapy in a 6-month period prior to the index date ([Table 7](#) NMOSD-Associated Conditions)

NMOSD-associated Conditions	Diagnosis ICD-9-CM Codes*	Diagnosis ICD-10-CM Codes*
Hypothyroidism	244.x	E89.0, E03.2, E03.8, E03.9
Pernicious anemia	281.0, 281.1	D51.x
Ulcerative colitis	556.x [excl. 556.2 and 556.3]	K51.xx [excl. K51.2x and K51.3x]
Myasthenia gravis	358.0x	G70.0x
Idiopathic thrombocytopenic purpura	446.6	M31.1
Hemiplegia/paraplegia	334.1, 342.x, 343.x, 344.0x-344.6x, 344.9	G11.4, G81.xx, G80.x, G83.0, G83.1x, G83.2x, G83.3x, G83.4, G83.9, G82.xx

NMOSD-associated Conditions	Diagnosis ICD-9-CM Codes*	Diagnosis ICD-10-CM Codes*
Bladder dysfunction	788.30, 788.31, 788.33, 788.34, 788.36, 788.37, 788.39-788.43, 596.xx	N30.xx, N31.x, N32.xx, N33
Neuropathic pain	353.x, 354.x, 355.x, 356.x, 357.x, 250.6, 729.2, 782	E08.40-E08.42, E09.40, E09.42, E10.40-E10.42, E11.40-E11.42, E13.40-E13.42, G50.0, G50.1, G54.x, G55.x, G56.x, G57.x, G58.x, G60.x, G61.x, G62.x, G63, G64, G65.x, G90.5x, M05.5x, M79.2, M54.1, R20
Antiphospholipid syndrome	289.81	D68.61
Sarcoidosis	135	D86.xx
Scleroderma	357.4, 359.6, 517.2, 701.0, 710.1	M34.xx, L90.0, L94.0, L94.1, L94.3
Sjogren's syndrome	710.2	M35.0x
Systemic lupus erythematosus	710	M32.xx
Dorsalgia	724.5	M54
Disorders of lipoprotein metabolism and other lipidemias	272.0, 272.1, 272.2, 272.3, 272.4, 272.5, 272.9	E78
Other acute disseminated demyelination	341.9	G36.9
Disorders of refraction and accommodation	367	H52
Visual disturbances	368	H53
Disturbances of skin sensation	782	R20
Somatoform disorders	300.81	F45
Other dorsopathies, not elsewhere classified	723.2, 723.3, 723.8, 723.9	M53

Abbreviations: ICD-9/ICD-10, 9th/10th Revision of International Classification of Diseases; CM, Clinical Modification; NMOSD, Neuromyelitis optica spectrum disorder

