The use of **add-on therapies** will be identified by administration/prescription/dispensation of other NMOSD maintenance or other immunosuppressive drug(s) (Table 9 and Table 10) during any of inebilizumab exposure period (2D). Corticosteroid pre-medication before inebilizumab infusion (used to reduce potential infusion reactions) will not be considered as an add-on therapy.

Figure 2 Inebilizumab treatment patterns

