	6A551Z3 - Pheresis of Plasma, Multiple	ICD-10-PCS
	8-820 Therapeutic plasmapheresis	OPS

Abbreviations: ATC, Anatomical therapeutic chemical; ICD-10: 10th Revision of International Classification of Diseases; OPS, operation and procedure classification system, PCS, Procedure Coding System

* Only intravenous administrations

Table 9 NMOSD Maintenance Therapies

Name of Agent	Description	Coding
1. Oral Steroids	H02 - Corticosteroids for systemic use	ATC
2. Immunosuppressive therapies		
a. Azathioprine	L04AX01	ATC
b. Mitoxantrone	L01DB07	ATC
c. Mycophenolate Mofetil	L04AA06	ATC
d. Methotrexate	L01BA01; L04AX03	ATC
e. Cyclophosphamide	L01AA01	ATC
3. B-Cell Targeting Therapy (anti-CD20)		
a. Ocrelizumab	L04AA36 /L04AG08 from 2024	ATC
	6-00a.e Atezolizumab, parenteral	OPS
b. Ofatumumab	L04AA52/ L04AG12 from 2024	ATC
	6-006.4 Ofatumumab, parenteral	OPS
c. Rituximab	L01FA01	ATC
	6-001.h Rituximab, intravenously	OPS
	6-001.j Rituximab, subcutaneous	
4. Tocilizumab	L04AC07	ATC
	6-005.m Tocilizumab, intravenously	OPS
	6-005.n 8 Tocilizumab, subcutaneous	
5. Eculizumab	L04AA25/L04AJ01 from 2024	ATC
	6-003.h Eculizumab, parenteral	OPS
6. Satralizumab	L04AC19	ATC

Abbreviations: ATC, Anatomical therapeutic chemical; NMOSD, Neuromyelitis optica spectrum disorder; OPS, operation and procedure classification system

Table 10 Other Immunosuppressive Drugs of Interest

Name of Agent	Description	Coding
1. Interferon beta-1a and 1b	L03AB07; L03AB08	ATC
2. Dimethyl-fumarate	L04AX07; L04AX09	ATC
3. Alemtuzumab	L04AA34/L04AG06 from 2024	ATC
	6-001.0 Alemtuzumab, parenteral	OPS
4. Fingolimod	L04AA27/L04AE01 from 2024	ATC
5. Natalizumab	L04AA23/L04AG03 from 2024	ATC
	6-003.f Natalizumab, parenteral	OPS
6. Glatiramer acetate	L03AX13	ATC
7. Peginterferon beta-1a	L03AB13	ATC
8. Teriflunomide	L04AA31/L04AK02 from 2024	ATC
9. Bortezomib	L01XG01	ATC
	6-001.9 Bortezomib, parenteral	OPS
10. Cladribine	L01BB04; L04AA40	ATC
	6-00a.4 Cladribine, oral	OPS
11. Daclizumab	L04AC0	ATC
	6-009.9 Daclizumab, parenteral	OPS
12. Ozanimod	L04AA38/L04AE02 from 2024	ATC
13. Siponimod	L04AA42/L04AE03 from 2024	ATC
14. Tacrolimus	L04AD02	ATC

Abbreviations: ATC, Anatomical therapeutic chemical; OPS: operation and procedure classification system

Table 11 Pain Medication

Name of Agent	Description	Coding
1. Anti-inflammatory and antirheumatic drugs	M01	ATC
2. Topical products for joint and muscular pain	M02	ATC
3. Muscle relaxants	M03	ATC
4. Anesthetic drugs	N01	ATC
5. Analgesics	N02	ATC

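### Corticosteroid premedication is excluded from add-on therapy but not from the concomitant-immunosuppressant subgroup built on the same drug tables, and the baseline windows disagree on whether the index day counts

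*Protocol*

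**What the plan says.** Protocol Section 6.7.2 names two subgroups of special interest. One is "patients concomitantly receiving other immunosuppressive agents", with membership taken from Tables 9 and 10 of Annex 3. The other is "patients aged >65 years at the index date, if the sample size permits". The index date is attached to age only; no date or window is given for concomitant use.

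Section 6.3.3 defines add-on therapy from the same Tables 9 and 10, tied to the inebilizumab exposure periods, and then adds: "Corticosteroid pre-medication before inebilizumab infusion (used to reduce potential infusion reactions) will not be considered as an add-on therapy". The exclusion appears nowhere else.

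In Table 9 the first row is "1. Oral Steroids", described and coded as "H02 - Corticosteroids for systemic use", with no route limit. Table 8 (acute treatments) uses the same H02 code for intravenous corticosteroids and has a footnote restricting it to intravenous administrations.

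For previous immunosuppressive therapies, Section 6.1 uses "a short period of 6 months prior to or at index date". Section 6.3.2 takes baseline acute treatments from the 6 months before the index date and applies the same period to maintenance therapy, without mentioning the index day.

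For relapse history, Section 6.3.2 offers, as one example for sources to use, "considering the previous use of acute treatments such as intravenous corticosteroids, intravenous immunoglobulin or plasmapheresis therapy", and leaves the detail to the SAP.

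**The concern.** The exclusion in Section 6.3.3 shows that the authors expected premedication to appear among the Table 9 and 10 records. The subgroup uses those tables without the exclusion, so as written a patient can qualify solely through a steroid given to prepare for the inebilizumab infusion.

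This is one of only two subgroups of special interest, and all three objectives are to be reported in it. Section 6.9 notes that other immunosuppressive therapies may themselves raise the risk of malignancy or serious infection. The subgroup is informative only if it contains patients who really are co-treated. Patients admitted through premedication alone pull its results towards those of the whole cohort. The disagreement over the index day leads to the same error in the description of previous therapy. Results are produced by data source, so sites may resolve these gaps differently.

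**Working it through.** **Definitions side by side**

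| Use of the drug lists | Section | Tables | Time window | Premedication excluded? |
|---|---|---|---|---|
| Add-on therapy | 6.3.3 | 9 and 10 | During an inebilizumab exposure period | Yes |
| Concomitant-immunosuppressant subgroup | 6.7.2 | 9 and 10 | None stated | No |
| Previous immunosuppressive therapies | 6.1 | Not cited there | 6 months, index date included | No |
| Baseline acute treatment | 6.3.2 | 8 | 6 months before index | No |
| Baseline maintenance therapy | 6.3.2 | 9 and 10 | Same period as acute treatment | No |

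**Which premedication reaches which list.** The protocol does not state the route of premedication.
- Oral premedication falls in Table 9 by its label, and so reaches the subgroup and baseline maintenance therapy.
- Intravenous premedication falls in Table 8 by its footnote, and so reaches baseline acute treatment and any relapse proxy built on it. It reaches Table 9 only if H02 is applied without route or route is not recorded.
- One record therefore affects both lists only where route is ignored or missing.

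**Index day.** Premedication on the day of the first infusion is inside the Section 6.1 window and outside the Section 6.3.2 window. Premedication dispensed shortly before the first infusion is inside both.

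**Whether a time anchor alone would be enough.** If membership were judged at the index date without the exclusion, index-day premedication would still count as concomitant use. The anchor and the exclusion are both needed.

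**The planning size.** Section 6.5 uses 400 patients. Its Table 3 follows from n = 1.96² × p(1 − p) / d²:
- p = 1%, d = 1%: 380.3 (stated 380)
- p = 4%, d = 2%: 368.8 (stated 369)

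These figures are not in dispute; 400 serves only as the base below.

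**How the effect scales.** Let f be the share of true co-users and c the share of the remaining patients admitted by a recorded premedication. Both are assumptions; the protocol gives neither.

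Subgroup size = 400 × [f + (1 − f)c]; share of true co-users = f / [f + (1 − f)c].

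| f | c = 0 | c = 25% | c = 50% | c = 100% |
|---|---|---|---|---|
| 10% | 40 (100%) | 130 (31%) | 220 (18%) | 400 (10%) |
| 20% | 80 (100%) | 160 (50%) | 240 (33%) | 400 (20%) |
| 50% | 200 (100%) | 250 (80%) | 300 (67%) | 400 (50%) |

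Entries are subgroup size, with the share of true co-users in brackets. The range runs from no effect (c = 0) to a subgroup identical to the cohort (c = 100%). The protocol does not say where in that range the study will fall.

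**The case against.** The strongest reply is that Section 6.7.1 leaves full definitions of exposures, covariates and subgroups to the SAP, and Section 6.3.2 does the same for relapses. Section 5 also lists both subgroups under the description of patients at first treatment, which favours an index-date reading for objective 1. This answers much of the missing time anchor. It does not answer the premedication mismatch, because the protocol has already fixed the drug tables, the H02 code and the single place where premedication is excluded. A SAP that follows the text faithfully would carry the mismatch forward.

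The second reply is that the label on the Table 9 row splits H02 by route. That stands and narrows the problem: intravenous premedication enters the subgroup only where route is not applied or not recorded.

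A reader might infer three stronger things that the documents do not support.
- *The subgroup becomes nearly the whole cohort.* That needs near-complete capture of premedication. Section 6.4.1 says the only in-hospital prescriptions in the French claims data are those for certain expensive drugs, so steroids given in hospital would probably not be seen there. France supplies 53,179,816 of the 110,687,896 adults in Table 4 (48%). Dutch inpatient pharmacy data cover about 10% of the population (Section 6.4.5). Steroids dispensed to outpatients could still appear.
- *Immortal time lowers the subgroup's AESI rate.* The protocol does not say that later co-treatment defines membership. Even if it did, follow-up under Section 6.1 does not end at an AESI. A patient with an infection in month 2 and co-treatment from month 6 would be in the subgroup with the event counted. Time before co-treatment would be misattributed, but no direction of bias follows.
- *Premedication will be counted as relapse.* The corticosteroid proxy is only an example, and its definition is left to the SAP.

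The study is also descriptive, and Section 6.9 disclaims causal assessment. That limits the consequences but does not make a misdefined subgroup acceptable.

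**Conclusion.** The point holds as an internal inconsistency. Sections 6.3.3 and 6.7.2 use the same tables, only the former excludes premedication, and Table 9 codes oral steroids with an H02 entry that has no route restriction. A premedication record falling under H02 can put a patient who uses no other immunosuppressant into the subgroup. Separately, Sections 6.1 and 6.3.2 disagree on whether the index day belongs to the window for previous therapy.

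The size is unknown. It depends on the route of premedication, on how often each source records it, and on the true share of co-users, none of which the protocol gives. AESI estimates in the overall population are not affected; the subgroup results and the baseline description of therapy are. It should be corrected before the SAP is finalised.

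**What to change.** 1. In Section 6.7.2, apply the premedication exclusion of Section 6.3.3 to the subgroup. In Section 6.3.2, apply it to baseline acute and maintenance therapy, and to any intravenous-corticosteroid relapse proxy that the SAP adopts. The SAP should say how many days before an infusion a steroid record is treated as premedication.
2. Add an oral-route restriction to H02 in Table 9 where route is recorded, mirroring the footnote to Table 8, and state how H02 is handled in sources without route.
3. Reconcile Sections 6.1 and 6.3.2 on whether the index day is in the previous-therapy window.
4. Judge subgroup membership at the index date, as for age. If later co-treatment is to count, attribute AESI person-time to the subgroup only from the start of that co-treatment.

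This takes a few sentences and no new data. The price is a somewhat smaller subgroup with wider intervals, and some residual misclassification where route is not recorded.

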6.7.2.1 Objective 1: New inebilizumab users' characterization

For objective 1, all new inebilizumab users (as defined in [section 6.3.1](#)) included in the study, regardless of the follow-up time will be described in terms of demographics, comorbidities, NMOSD-related clinical characteristics, previous immunosuppressive therapies, and inebilizumab initiation characteristics (including information on prescriber and treatment indication). Characterization will consist of summary statistics for continuous and categorical variables, as described in [section 6.7.1](#).

6.7.2.2 Objective 2: Treatment patterns of inebilizumab

The number and proportion of patients in the overall study population receiving the drug, and by dose stratification, (below or above the recommended dose in the product characteristics [300 mg/IV infusion]) will be reported at each of the first, second, and third infusion. Additionally, the number and proportion of patients who change dose between the individual infusions as well as the time (in days) between the first and each subsequent treatment (regardless of dose) will be reported.

Inebilizumab treatment patterns, as described below, will be assessed in the period of 12 months from index date and only patients with a complete 12-month follow-up, regardless of inebilizumab discontinuation, will be considered.

The number and proportion of patients who experience the following treatment pattern related events will be reported separately for each of the events: continuous and discontinuous treatment, switching, use of add-on therapies, according to what is defined in [section 6.3.3](#). For all the events, the denominator consists of all patients exposed to inebilizumab and followed for the full 12-month period.

The median time to switching and the median time to use of add-on drugs will be described in the subgroups of switchers and patients using add-on therapies (as defined in [section 6.3.3](#)), respectively. For the subgroup of switchers (as defined in [section 6.3.3](#)), the time to switch will be calculated as the time from the index date until the first recorded start date of another NMOSD maintenance drug. For the subgroup of patients using add-on therapies (as defined in [section 6.3.3](#)), the time to add-on drug use will be calculated as the time from the index date until the first recorded start date of an add-on drug.

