6.3.3 Treatment patterns

During follow-up, treatment patterns will be characterized in terms of dose, treatment duration, frequency of drug discontinuation, switching and use of add-on therapies. All patients included in the study will be deemed exposed (at least one inebilizumab treatment), but only those with complete 12-month follow-up will be considered in the evaluation of the treatment patterns as described below.

According to the product specifications, the 12-month follow-up will cover 3 potential inebilizumab administrations: initial intravenous (IV) infusion followed by a second

infusion 2 weeks later and a subsequent infusion 6 months after the first treatment (Figure 2A). The first and third infusion will be considered in defining inebilizumab treatment patterns.

Treatment duration will be the sum of days under inebilizumab exposure during the follow-up. Number of days under exposure will be calculated for the first and the third infusion as the difference between end date of inebilizumab exposure period and the administration/prescription/dispensation date (Figure 2B).

[figure not shown]
Inebilizumab complete **exposure period** will be assumed to last 180 days after drug administration/prescription/dispensation. The **end date of the exposure** period will be defined as the end of each inebilizumab exposure period within follow-up or the end date of follow-up if comes first (Figure 2B).

A patient will be considered to be in inebilizumab **continuous use** if no gap longer than 60 days occurs between the end date of the first inebilizumab exposure period and the beginning of the third (2B). **Temporary discontinuation** (intermittent users) will be defined in patients with gaps between inebilizumab exposure periods longer than 60 days but with a subsequent inebilizumab administration/prescription/dispensation during the follow-up. A patient will be defined as having **permanently discontinued** inebilizumab if no subsequent inebilizumab treatment is registered during the follow-up after the end date of the first inebilizumab exposure period.

Switchers will be a subgroup of patients who discontinue inebilizumab (temporarily or permanently) during the follow-up and have other NMOSD maintenance drug administered/ prescribed (Table 9) after the end date of inebilizumab exposure period (2C). The alternative NMOSD drugs will be described.

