6.9 Limitations of Research Methods

Automated healthcare databases are appropriate for real-world studies due to the recording of prescriptions and clinical data from routine clinical practice, independently of any study purposes.

The use of secondary data allows the identification of all drug users which limits selection bias, since all patients fulfilling the inclusion criteria are included in the study. Inebilizumab is available in secondary care settings (hospitals and specialized centers) which narrows down the area of searching for eligible patients. This is particularly relevant to answer the research objectives due to the fact NMOSD is a rare condition and inebilizumab is expected to be used by a small number of individuals. Furthermore, the

inclusion of several countries contributes to the representativeness of European inebilizumab users.

However, some limitations should be addressed:

- Inebilizumab is a novel drug, so one can expect changes over time in clinical practice regarding the use of the drug. The uptake of inebilizumab in the population covered by the data sources may be slow at the beginning of the study period and is likely to increase closer to the end. This pattern may result in a small sample of patients with complete follow-up, i.e., eligible to answer objectives 2 and 3. Thus, treatment patterns and safety outcomes may lack precision. Additionally, long-term treatment patterns and safety outcomes will not be assessed in this study.
- Despite the anticipated high reliability and validity of the data sources proposed for the study, there may be a potential of under- or misreporting of diagnostic information. In addition to variation in ICD-10 coding practices across countries, NMOSD is a rare and complex condition, with wide extent of the diagnostic work-up and diverse diseases can mimic NMOSD (39), making a late diagnosis or potential misclassification more probable. NMOSD-associated conditions may also be prone to misclassification, particularly the less severe ones, which may underestimate their frequency.
- Data collected for administrative purposes may be incomplete for medical information not directly related to reimbursement. This can affect the measurement of variables to characterize inebilizumab users and safety outcomes, underestimating its frequency. When available, the use of disease registries may minimize this limitation.

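### Section 6.7.2.2 takes third-infusion receipt over all starters, against the complete 12-month restriction stated elsewhere; as written, it counts patients whose follow-up ended before month 6 as non-receivers

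*Protocol*

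**What the plan says.** The first paragraph of section 6.7.2.2 sets the analysis of receipt and dose: "The number and proportion of patients in the overall study population receiving the drug, and by dose stratification", a result that "will be reported at each of the first, second, and third infusion". The restriction on follow-up comes only in the next paragraph: "Inebilizumab treatment patterns, as described below, will be assessed in the period of 12 months from index date", with complete follow-up required. The explicit denominator follows a list of events (continuous and discontinuous treatment, switching, add-on therapy): "For all the events, the denominator consists of all patients exposed to inebilizumab and followed for the full 12-month period". Receipt of an infusion is not in that list.

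Section 6.3.3 points the other way. It states that "treatment patterns will be characterized in terms of dose, treatment duration, frequency of drug discontinuation, switching and use of add-on therapies", and then that "only those with complete 12-month follow-up will be considered in the evaluation of the treatment patterns as described below". The Data analysis part of the Abstract also confines treatment patterns to patients with 12 months of complete follow-up. Section 6.9 describes patients with complete follow-up as the ones eligible for Objectives 2 and 3, and section 5 places dosing under Objective 2.

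On accrual, section 6.1 says: "Patients initiating the treatment will be identified throughout the study period". Follow-up is 12 months, cut short by the end of the study period, death or disenrolment. Section 6.3.3 places the second infusion 2 weeks after the first and the third 6 months after it.

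**The concern.** The two rules cannot both be applied to the same table, and the one in the analysis section is the one that distorts the result. A patient who starts three months before the data end, or who leaves in month 4, cannot be seen to receive a third infusion. That patient still counts in an all-starters denominator. The reported proportion then mixes not receiving the drug with running out of data, and the dose split at the third infusion inherits the same denominator.

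The error can only lower the proportion, and a larger cohort does not remove it. Section 6.7.1 has descriptive analyses run by country or data source, and Table 1 gives study periods of 41 to 57 months. Part of any difference between countries in third-infusion receipt would therefore come from the length of the data window.

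**Working it through.** The protocol states no figure for the proportion receiving the second or third infusion, so there is none to reproduce. The calculation asks what share of starters reach the end of the study period before an infusion falls due.

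**Inputs**
- Study period T in months (Table 1): France 57, Germany 54, Italy 56, Netherlands 41, Spain 53. Counting the calendar months inclusively from the stated start and end dates gives 56 for France and 53 for Germany, and agrees for the other three. The one-month difference is immaterial here (6/56 = 10.7% against 6/57 = 10.5%).
- Time to the infusion, d (section 6.3.3): third, 6 months; second, 14 days = 14/30.4375 = 0.46 months.
- Shape of uptake: not given in figures. Section 6.9 says only that it "may be slow at the beginning of the study period and is likely to increase closer to the end". Two shapes are assumed: uniform, and rising linearly from zero at the start of the study period.
- No deaths or disenrolment are modelled.

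**Formulas**
- Uniform starts: share not yet due = d/T.
- Linearly rising starts: share not yet due = 1 − ((T − d)/T)².
- Reported proportion = proportion among those due × (1 − share not yet due).

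**Third infusion (d = 6)**

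| Country | Uniform | Linearly rising |
|---|---|---|
| France | 6/57 = 10.5% | 1 − (51/57)² = 19.9% |
| Germany | 6/54 = 11.1% | 1 − (48/54)² = 21.0% |
| Italy | 6/56 = 10.7% | 1 − (50/56)² = 20.3% |
| Netherlands | 6/41 = 14.6% | 1 − (35/41)² = 27.1% |
| Spain | 6/53 = 11.3% | 1 − (47/53)² = 21.4% |

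If every patient who was due received the third infusion, the table would show 85.4% to 89.5% under uniform starts and 72.9% to 80.1% under rising starts. If 90% of those due received it, the extremes would be 0.90 × 0.895 = 80.5% and 0.90 × 0.729 = 65.6%.

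Per 400 patients, the cohort size used for illustration in section 6.5, the lowest share is 0.105 × 400 = 42 patients and the highest is 0.271 × 400 = 108. The upper figure would need every patient to follow the Dutch window with rising starts, so a pooled cohort would lie below it.

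**Second infusion (d = 0.46)**
- Uniform: 0.46/57 = 0.8% to 0.46/41 = 1.1%.
- Rising: 1.6% (France) to 2.2% (Netherlands).

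**The case against.** The best defence is that the restriction is already in the protocol. The Abstract and sections 6.3.3 and 6.9 state it, and section 6.3.3 names dose first among the treatment patterns. Section 6.7.2.1 says explicitly that Objective 1 uses patients whatever their follow-up time, and section 6.7.2.2 carries no such phrase. Elsewhere, as in sections 5 and 6.7.2, the overall study population is set against the sub-groups (concomitant immunosuppressants, age over 65), so the term need not mean all starters irrespective of follow-up. If those passages govern, no bias arises.

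This stands to the extent that a reader may not infer that the protocol has settled on the all-starters denominator. It does not remove the point. The opening paragraph of section 6.7.2.2 mentions no sub-group, and its restriction is worded to cover what comes after it. Table 5, although it belongs to Objective 3, lists the overall population and patients with complete 12-month follow-up as two different populations. Two programmers could each defend a different table. The matter is also not simply left to the SAP, because the protocol itself names the denominator.

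A reader might also infer that the study's persistence results are biased. The documents do not support that. Continuous use and temporary and permanent discontinuation are the protocol's own persistence measures, and they have an explicit complete 12-month denominator. They would differ from third-infusion receipt even with the same denominator, because continuous use adds a 60-day gap rule.

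Finally, the study is descriptive and the upper range rests on an assumed linear rise. Section 6.9 expects uptake to increase but gives no shape. Under uniform starts the spread between countries is about 4 points (10.5% to 14.6%).

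**Conclusion.** The point holds as a contradiction between section 6.7.2.2 and the Abstract, section 6.3.3 and section 6.9, in which the operative analysis text gives the biased version. Followed as written, it would count about 11-15% of starters by country (uniform starts), or about 20-27% (linear rise), as not having received the third infusion only because the data ended. These figures assume that no one is lost before month 6 and that the infusion falls exactly at 6 months. Death and disenrolment before then would increase them.

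The substance is confined to the third infusion and its dose split. A reader might extend the concern equally to the second infusion, but 1-2% is close to negligible.

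**What to change.** State one population for the receipt and dose paragraph of section 6.7.2.2 and align it with section 6.3.3 and the Abstract.

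- First infusion: keep all patients.
- Third infusion, and the second for consistency: use the already defined population with complete 12-month follow-up, or only patients followed to at least day 240 (the protocol's 180-day exposure period plus its 60-day gap), regardless of receipt.
- Alternative for the third infusion: the cumulative incidence of receipt by day 240, with administrative censoring and death as a competing event. This keeps a patient who dies before the infusion as a non-receiver, whereas the two fixed populations leave that patient out, so the report should say which quantity is meant.

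Do not add to a day-240 denominator patients who received the infusion but were censored before day 240. That keeps early-censored receivers, drops early-censored non-receivers and biases the proportion upward.

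The cost is about two sentences of text and a smaller denominator for the later infusions. On the same assumptions, with 240/30.4375 = 7.9 months, the day-240 rule sets aside 13.8% to 19.2% of starters (uniform) or 25.8% to 34.8% (rising). The 12-month rule sets aside 12/57 = 21.1% to 12/41 = 29.3% (uniform), or 37.7% to 50.0% (rising). The day-240 rule therefore keeps more patients, while the 12-month rule matches the denominator of the other treatment patterns.
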